Clinical investigation plan

**C19-658
(EX-MKTG-108)**

**A clinical evaluation of two contact lenses used with
three care systems**

**A clinical evaluation for
CooperVision Inc.**

[figure not shown]
**Principal Investigator
[name]**

June 2019

Contents

Document control	3
Study summary	
Section 1. Overview	6
1.1 Background	6
1.2 Personnel	6
1.3 Study objectives	6
1.4 Study design	6
1.5 Statistical considerations	6
1.6 Risk analysis	7
Section 2. Resources	8
2.1 Subject selection	8
2.2 Subject discontinuation	9
2.3 Safety parameters, adverse events and concurrent illnesses	9
2.4 Study termination	10
2.5 Protocol deviations	10
2.6 Study resources	10
2.7 Study control	11
2.8 Documentation	11
2.9 Data collection and analysis	11
2.10 Study completion	11
2.11 Confidentiality	12
2.12 Study monitoring	12
Section 3. Subject management	13
3.1 Visit scheduling	13
3.2 Visit conduct	13
3.3 Monitoring subject compliance	18
3.4 Missing, unused and spurious data	18
Section 4. Study co-ordination	19
4.1 Document processing	19
4.2 Disclosure	19
4.3 Personnel	19

Study summary

This open-label, randomised, crossover study will compare the clinical performance and subjective acceptance of the two lens brands (Biofinity and Avaira Vitality) when used with three care systems (Hy-Care, All in One Light, and Refine One Step).

Thirty subjects will be enrolled on this study and will use each lens/solution combination in random sequence for one month each. The following will be assessed throughout the study: ocular physiology, [REDACTED] and subjective response.

A study summary is shown in Table 1.

Visit	Procedures
Information and consent presentation Initial visit	Short on-line presentation of study aims and procedures Informed consent taken Ocular and contact lens history Medical history Questions on contact lens/solution aftercare [REDACTED] Pre-corneal NIBU I [REDACTED] Fitting of first lens pair [REDACTED] Subjective scores
1 month visit	Issue study lenses and first solution Record wear times/medical/ocular history Retrieval of study products Subjective scores and questions [REDACTED] [REDACTED] Fitting of second lens pair [REDACTED] Subjective scores
2 month visit	Issue study lenses and second solution Record wear times/medical/ocular history Retrieval of study products Subjective scores and questions [REDACTED] [REDACTED] Fitting of third lens pair [REDACTED] [REDACTED]
3 month visit	Issue study lenses and third solution Record wear times/medical/ocular history Retrieval of study products Subjective scores and questions [REDACTED] [REDACTED] Fitting of fourth lens pair [REDACTED] Subjective scores Issue study lenses and fourth solution

4 month visit
	
Record wear times/medical/ocular history Retrieval of study products Subjective scores and questions [REDACTED] Fitting of fifth lens pair [REDACTED]

5 month visit
	
Subjective scores Issue study lenses and fifth solution Record wear times/medical/ocular history Retrieval of study products Subjective scores and questions [REDACTED] Fitting of sixth lens pair [REDACTED]

6 month visit
	
Subjective scores Issue study lenses and sixth solution Record wear times/medical/ocular history Retrieval of study products Subjective scores and questions Visual acuity [REDACTED] [REDACTED] Exit form signed and payment issued

Table 1: Study summary.

Section 1. Overview

1.1 Background

The performance of different contact lens brands may vary when used with certain types of contact lens care systems. This includes the level of corneal staining seen at follow-up visits and may also include other measures of lens performance including subjective comfort and surface deposition. This project will evaluate two key CooperVision monthly replacement lens brands (Biofinity and Avaira Vitality) when used with three CooperVision care systems (Hy-Care, All in One Light, Refine One Step).

1.3 Study objectives

This study aims to compare the clinical performance of the Biofinity and Avaira Vitality lenses when used in combination with three care systems (Hy-Care, All in One Light and Refine One Step).

1.4 Study design

This will be a randomised, open-label, crossover study, controlled by cross-comparison. Thirty subjects will use each lens and solution combination for a month in random sequence; that is for a total of six months. Follow-up visits for each lens will be performed after one month of wear. Lenses will be worn on a daily wear, reusable wear schedule.

1.5 Statistical considerations

The principal hypothesis to be tested in this work is [REDACTED] subjective scores for the lenses will be substantially equivalent.

[REDACTED] subjective responses will generate data that are likely to be continuous and normally distributed. As such, these will be compared using linear regression models or other parametric methods. Subjective preferences will be compared using chi-squared tests. Lens fit data are expected to be ordinal data and assessed with non-parametric approaches. Deviations from this statistical plan will be discussed in the final report. Deviations may be necessary due to differences between the actual data distribution compared with the anticipated data distribution.

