1.5.1 Power analysis

Using subjective comfort data from a previous, similar study, 22 subjects are required to complete the study for 80% power, assuming a difference of 10 points and a deviation of 16 points on a 0-100 scale. To allow for discontinuations, 30 subjects will be dispensed.

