3.2 Visit conduct

3.2.1 Initial visit

Prior to the dispensing visit, each subject will receive a study-specific information form outlining the study at least 24 hours before the consent visit and will be asked to watch a short on-line information presentation detailing study visits and procedures. They will be asked to complete several multiple-choice questions to gauge their understanding of the study. Upon successful completion of these questions, the subject will be booked to attend the Dispensing 1 visit. Subjects should attend this visit wearing their spectacles.

- 8. [REDACTED]
- 9. [REDACTED]

Classification	Primary signs	Secondary signs
Signs	[REDACTED]	[REDACTED]
Scale	Efron Grading Scales (scored to nearest 0.1)	Efron Grading Scales (scored to nearest 0.1) (except mucin balls, where the number is recorded).

Table 5: Biomicroscopic signs. Staining assessed with sodium fluorescein.

- 10. The presence of any adverse events will be recorded [REDACTED]
- 11. The investigator will confirm that the subject satisfies all the inclusion and exclusion criteria. Subjects who fail to meet all the criteria at this time will usually be discontinued and replaced.
- 12. The first randomised lens pair will be fitted and allowed to settle for five minutes.
- 13. [REDACTED]
- 14. [REDACTED]
- 15. [REDACTED]
- 16. [REDACTED]

17. The subject will be asked to score the following subjective scores with reference to appropriate vertical visual analogue scales (0-100) [REDACTED]

- Comfort
- Vision
- Burning/stinging
- Overall score

18. The subject will be issued with a supply of contact lenses for the first study period, and with the first solution.

19. The subject will then be discharged and asked to return for the one-month follow-up visit [REDACTED]

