3.2.2 One month visit

[REDACTED]

[REDACTED] The following procedures will be performed (any ocular measurement procedures outlined below will be carried out on each eye):

1. Any medical or ocular issues since the last visit will be recorded.
2. [REDACTED]
3. [REDACTED]
4. Retrieval of any unused lenses, plus solution and case.
5. The subject will be asked to score the following with reference to appropriate vertical visual analogue scales (0-100) [REDACTED]
 - Comfort after insertion
 - Comfort before removal
 - Overall comfort
 - Vision
 - Variable vision
 - Vision at night
 - Dryness
 - Ocular redness
 - Burning/stinging
 - Ease of lens insertion
 - Ease of lens removal
 - [REDACTED]
 - [REDACTED]

- [REDACTED]
6. The presence of the following [REDACTED]
- [REDACTED]
 - [REDACTED]
 - [REDACTED]
 - [REDACTED]
 - [REDACTED]
 - Burning
 - [REDACTED]
 - Variable vision
 - [REDACTED]
 - [REDACTED]
 - [REDACTED]
 - [REDACTED]
 - [REDACTED]
7. [REDACTED]
- [REDACTED]
 - [REDACTED]
 - [REDACTED]
 - [REDACTED]
- [REDACTED]
- [REDACTED]
- [REDACTED]
9. [REDACTED]
- [REDACTED]
- [REDACTED]
11. [REDACTED]
12. [REDACTED]
13. The lenses will then be removed and discarded.
14. [REDACTED]
- [REDACTED]
15. The same procedures as for the initial visit (3.2.1) points 6-15 will be carried out, with the second pair of lenses and second solution dispensed.

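### The principal hypothesis is that subjective scores are equivalent, but the readable plan gives only a comparison and no rule for concluding equivalence

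*Combined protocol and SAP*

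**What the plan says.** Section 1.5 (Statistical considerations) states the principal hypothesis as "subjective scores for the lenses will be substantially equivalent". A redaction falls inside that sentence, just before these words, and another opens the next paragraph. On method, the readable text says of the subjective responses that "these will be compared using linear regression models or other parametric methods". No equivalence test, margin, confidence level or decision rule is readable.

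Section 1.5.1 (Power analysis), which shows no redaction, takes its figures from comfort scores in an earlier study, recorded from 0 to 100. It states: "22 subjects are required to complete the study for 80% power, assuming a difference of 10 points and a deviation of 16 points". The section then covers dropout: "To allow for discontinuations, 30 subjects will be dispensed". It does not name the test or alpha, and does not say whether 10 points is an equivalence margin or a difference to be detected.

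The design is a six-period crossover (section 1.4): "Thirty subjects will use each lens and solution combination for a month in random sequence". The objective in section 1.3 is to compare the "Biofinity and Avaira Vitality lenses when used in combination with three care systems". Section 3.2.2 records three comfort scores at one month: after insertion, before removal and overall. Section 1.5.1 does not say which one it refers to.

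**The concern.** A hypothesis of equivalence needs a criterion that the data can meet or fail. A plain comparison supplies none. A non-significant difference may mean that the lenses perform alike, or only that completers were few or scores noisy. If non-significance were taken as support, the chance of wrongly supporting equivalence would rise as the study lost subjects. Under a confidence-interval rule it would not.

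What is at stake is the main conclusion of the study. Some observed differences would count as support under one reading and not under the other, and nothing readable fixes the choice before the data are seen. A reader also cannot tell from section 1.5.1 whether the 80% power belongs to the hypothesis as worded or to a test for a difference.

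**Working it through.** **Inputs.** From section 1.5.1: 22 completers, 80% power, difference 10, deviation 16, 30 dispensed. Assumed, because not stated: 16 is the SD of within-subject differences; one lens contrast; a difference test at two-sided 5%, or TOST at 5% per side with margin 10 and true difference 0.

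**1. Reproducing 22.**
- Difference test, normal approximation: n = [(1.960 + 0.842) × 16/10]² = 20.1. The exact paired t-test has 79.8% power at 22 and 81.7% at 23.
- TOST, normal approximation: n = [(1.645 + 1.282) × 16/10]² = 21.9, which rounds up to 22. The exact paired calculation gives 76.6% at 22 and 81.5% at 24.

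Both readings are close to the stated figure, so it does not show which was meant.

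**2. Chance of a wrong reading at a true 10-point difference** (exact paired t).

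| Completers | Difference test non-significant | TOST, margin 10, declares equivalence |
|---|---|---|
| 22 | 1 − 0.798 = 20% | 5% |
| 30 | 1 − 0.911 = 9% | 5% |

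**3. The same contrast seen from the result** (observed SD 16).
- With 22 completers the standard error is 16/√22 = 3.41. The 95% half-width is 2.080 × 3.41 = 7.1, and the 90% half-width is 1.721 × 3.41 = 5.87. An observed difference up to 7.1 points is non-significant, but the ±10 rule passes only up to 10 − 5.87 = 4.1 points. The two readings conflict from 4.1 to 7.1 points.
- With 30 completers the half-widths are 5.97 and 4.96, so they conflict from 5.0 to 6.0 points.

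**4. If 16 is the SD of single scores.** The SD of differences is then 16√[2(1 − ρ)], which is 19.6, 16.0 or 11.3 for a within-subject correlation of 0.25, 0.5 or 0.75. With 22 completers, a true 10-point difference is non-significant in 37%, 20% or 2% of trials.

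**5. Power of an equivalence rule** (margin 10, SD 16, true difference 0).

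| Rule | 22 completers | 30 completers |
|---|---|---|
| One within-solution contrast, paired t, 5% per side | 77% | 91% |
| Same, linear model balanced over periods, 5% per side | 79% | 92% |
| Same, paired t, 2.5% per side | 60% | 82% |
| All three solutions must pass, balanced linear model, 5% per side | 51% | 78% |

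The linear model has subject, period, lens, solution and lens-by-solution terms, with 6n − n − 10 residual degrees of freedom (100 at 22, 140 at 30). The last row assumes independent solution-specific differences. Under the same assumption, a contrast averaged over the three solutions has SD 16/√3 = 9.2, and paired TOST power at 22 is about 99.9%.

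**The case against.** The strongest objection is redaction. It falls within the hypothesis sentence and at the start of the analysis paragraph, so hidden words may qualify the term equivalent or hold a criterion. This stands, and it limits the point to the readable text. The method sentence quoted above names no equivalence procedure, and the silence of section 1.5.1 on its test cannot be put down to redaction there.

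A second objection is that 10 points may well be the margin, since TOST by normal approximation gives exactly 22 after rounding. On that reading the study was sized for its hypothesis and the number merely lacks a label. This is plausible. A reader might infer the opposite, that 22 was sized for a difference test and is therefore wrong for the hypothesis. The documents do not support that, because 22 fits both readings.

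A third objection is that the harm is conditional, and that the 20% is only the complement of the planned 80% power. Both parts are true. A reader might infer that the plan intends to treat non-significance as equivalence, but it nowhere says so, and regression models can yield confidence intervals. What remains is that nothing readable rules that reading out.

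The questions of which SD, which comfort score and which contrast are missing detail to be settled along the way. They are not errors in themselves.

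**Conclusion.** The point holds for the readable plan and should be fixed. Equivalence is the principal hypothesis, and no readable rule says when it would be concluded. If non-significance were used as that rule, a true 10-point difference would pass in about 20% of trials with 22 completers or 9% with 30, against 5% under TOST with a 10-point margin.

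These figures assume an SD of within-subject differences of 16, one lens contrast and the alpha levels given above. The conflict zone also depends on a margin of 10, which the plan does not confirm. No error is shown in either 22 or 30. Confidence is medium because of the redactions. If a criterion exists in redacted text, a cross-reference from section 1.5.1 would close most of the point.

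**What to change.** In section 1.5, before data are seen, state that equivalence will be concluded only if the 90% confidence interval (two one-sided 5% tests) for the within-subject Biofinity minus Avaira Vitality difference lies wholly within a pre-stated margin. The interval should come from the planned linear model, for one named one-month comfort score. Say whether the contrast is averaged over solutions or taken within each, and if within each, whether all three must pass. The margin can be ±10 points if the sponsor confirms that section 1.5.1 meant a margin. Add that a non-significant difference will not be taken as equivalence. Otherwise, drop the equivalence wording and report the estimated differences with confidence intervals.

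In section 1.5.1, say which test the power is for, whether 10 is a margin or a detectable difference, and whether 16 is the SD of within-subject differences. Restate power for the chosen rule. Keep 30 subjects.

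The cost is wording only, with no added subjects, visits or procedures. The downside is power. For a single within-solution contrast with margin 10, it is about 77-79% at 22 completers and 91-92% at 30. It is lower at 2.5% per side or if every solution must pass, and much higher for a contrast averaged over solutions if the solution-specific differences are independent. A margin below 10 or a non-zero true difference would also lower it. The alternative wording gives up the equivalence claim.

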1.5.1 Power analysis

Using subjective comfort data from a previous, similar study, 22 subjects are required to complete the study for 80% power, assuming a difference of 10 points and a deviation of 16 points on a 0-100 scale. To allow for discontinuations, 30 subjects will be dispensed.

1.6 Risk analysis

This study is considered to be a non-significant risk study based on United State Food and Drug administration (FDA) and International Standards Organization (ISO) guidelines due to the daily wear nature of the study. With the potential benefit of this study, the work is considered to be ethically justifiable. Ethical approval will be sought from the University of Manchester Senate Committee on the Ethics of Research on Human Beings (hereafter referred to as Manchester UREC). The work where practical will be conducted in accordance with the ICH Good Clinical Practice Guidelines and the international standard BS EN ISO 14155:2011 'Clinical investigation of medical devices for human subjects'.

Section 2. Resources

2.1 Subject selection

In this work 30 subjects will be recruited and enrolled.

2.1.1 Subject withdrawal and replacement

This study includes seven clinical visits. Once the study consent form is signed, the subject is considered to be enrolled on the study. Subjects who have signed the consent form, but who have not completed the first dispensing visit will usually be replaced. All subject data will be included in the final analyses unless there are strong grounds for exclusion; such grounds will be detailed in the final report. At the end the study, all subjects will sign a study exit form.

2.1.2 Subject recruitment

Subjects will be recruited by one or more of following means:

1. Posting study details on The University of Manchester's 'Research Volunteers' website.
2. Correspondence to existing wearers on the Eurolens Research database of subjects.
3. Advertising through a variety of media via a format separately approved by Manchester UREC.

2.1.3 Inclusion criteria

Subjects will only be eligible for the study if:

1. They are aged 18-50 and have capacity to volunteer.
2. They understand their rights as a research subject and are willing and able to sign a Statement of Informed Consent.
3. They are willing and able to follow the protocol.
4. They are an existing wearer of reusable, single vision, spherical soft contact lenses.
5. They have a contact lens spherical prescription between -1.00 to -6.50D (inclusive)
6. They have a spectacle cylindrical correction of -1.00D or less in each eye.
7. At dispensing, they can attain at least 0.20 logMAR distance high contrast visual acuity in each eye with the study lenses within the available power range.
8. They are willing to comply with the wear schedule (at least five days per week and for at least eight hours per day).
9. They agree not to participate in other clinical research for the duration of the study.

2.1.4 Exclusion criteria

Subjects will not be eligible to take part in the study if:

1. They have an ocular disorder which would normally contra-indicate contact lens wear.
2. They have a systemic disorder which would normally contra-indicate contact lens wear.
3. They are using any topical medication such as eye drops or ointment.
4. They have had cataract surgery.
5. They have had corneal refractive surgery.
6. They have any corneal distortion resulting from previous hard or rigid lens wear or have keratoconus.
7. They are pregnant or breastfeeding.
8. They have any ocular abnormality which would, in the opinion of the investigator, normally contraindicate contact lens wear.
9. They have any infectious disease which would, in the opinion of the investigator, contraindicate contact lens wear or pose a risk to study personnel; or they have any immunosuppressive disease (e.g. HIV), or a history of anaphylaxis or severe allergic reaction.
10. They have taken part in any other contact lens or care solution clinical trial or research, within two weeks prior to starting this study.

2.2 Subject discontinuation

In general, subjects should be discontinued at any time, if it is in their best interests, as judged by the investigator. Reasons for this may include clinical signs of grade 3 or more, lack of motivation, discomfort, repeated refusal to follow instructions or the use of non-study products such as solutions or lenses. Subjects will be discontinued if a serious adverse event occurs or if they miss two or more planned consecutive visits. Subjects who fail to satisfy all the inclusion and exclusion criteria will be discontinued and replaced. Subjects may choose to leave the study at their own request. All discontinuations will be carefully recorded.

2.3 Safety parameters, adverse events and concurrent illnesses

The key safety parameters are the serious and significant ocular adverse events listed in

Clinical assessment is made at the study visit(s) for these parameters. The presence of any ocular adverse event will be reported on the case report forms and those described as 'serious' or 'significant' will be detailed in the final report. Similarly, any concurrent illness that is likely to impact on the relevance and quality of the captured data will be noted on the case report form.

2.3.1 Investigator obligations

At all times the investigator will act in the best interest of the subject. Referral or treatment of an adverse event or other clinical finding should be initiated in the best clinical judgement of the investigator, irrespective of the participation in the clinical study.

2.3.2 Reporting obligations

In the case of a 'serious' or 'significant' adverse event, the Principal Investigator will notify the Industrial Contact Person as soon as possible. Manchester UREC and any regulatory authorities will be informed as required.

2.4 Study termination

If it becomes necessary to terminate the study earlier than planned, the Industrial Contact Person will notify the Principal Investigator who will end the study with the cooperation of other staff members. Manchester UREC will be informed.

2.5 Protocol deviations

Any deviations from this protocol will be recorded, and reported to the Industrial Contact Person as appropriate. Manchester UREC will be informed as necessary.

2.5.1 Protocol amendments

Any amendments will be agreed between the Industrial Contact Person and the Principal Investigator with the cooperation of other staff members. Amendments will be recorded, identified and distributed. Approval from Manchester UREC will be obtained as necessary.

2.6 Study resources

Study products will be stored according to the manufacturer's product instructions.

